### 5.2 Exclusion Criteria

Subjects who meet any of the following criteria are ineligible for enrollment.

1. Subjects who have received intervening anti-cancer therapy (between their last dose of NKTR-102 and administration of the first dose of NKTR-102 in this extension study).

2. Subjects with 2 dose reductions of NKTR-102 and have a toxicity that requires another dose reduction.
3. Female subjects who are pregnant or lactating, who plan to get pregnant, or who have a positive pregnancy test at screening or during participation in this study.

### 5.3 Early Withdrawal/Discontinuation from Study

Subjects may choose to discontinue/withdraw from study drug treatment or the study at any time, for any reason, and without prejudice to further treatment. A subject who withdraws consent from study participation will be asked to state the level of withdrawal:

1. Withdrawal from treatment only; and/or
2. Withdrawal from contact during the post-treatment period (for off-study data, such as subsequent anti-cancer therapy or survival).

In the event of withdrawal of consent, the study staff and/or Investigator must make every effort to ascertain the level of consent withdrawn. An objective of this study is to assess survival status, so site personnel must ascertain if subjects will permit continued follow-up if consent is withdrawn. The type of consent withdrawal must be noted in source documents and CRF.

Subjects may stop NKTR-102 treatment or be withdrawn from the study for any of the following reasons, but will be followed for safety until resolution or permanent sequelae of all toxicities attributable to NKTR-102 (see Section 9.5):

- Progression of disease
- Adverse Event (unacceptable toxicity)
- Death
- Non-compliance of the subject with protocol-mandated procedures
- Withdrawal of consent by subject
- Physician (Investigator) Decision
- Lost to Follow-Up
- Study is terminated by the Sponsor

### 5.3.1 Withdrawal Procedures

In the event of a subject's withdrawal from treatment, the Investigator will promptly notify Nektar Therapeutics and will make every effort to complete the End-of-Treatment assessments and ascertain if subjects will permit continued follow-up (i.e., for survival status, subsequent anti-cancer therapy, and disease status). Before a subject is considered "Lost to follow-up", study personnel must attempt to contact the subject at least twice by phone and once by mail with documented receipt. Study personnel may use public records to check for mortality for any subjects considered "Lost to follow-up" or who have withdrawn consent from the study, if permitted by applicable laws or regulations.

## 6.0 INVESTIGATIONAL PRODUCT(S)/STUDY MEDICATIONS

### 6.1 Description and Formulation

The drug substance NKTR-102 is a polymeric conjugate prodrug of irinotecan with 3 essential components: a relatively large polymer, a biodegradable linker, and an active agent. In NKTR-102, irinotecan is attached to PEG via a releasable linker that is hydrolyzed in vivo to deliver irinotecan, which is further metabolized to the active metabolite, SN38. [Table 3](#) provides the nomenclature information for drug substance NKTR-102.

**Table 3: Nomenclature**

Compound Number/Name:	NKTR-102 (etirinotecan pegol)
Sponsor:	Nektar Therapeutics
Chemical classification:	Topoisomerase 1 Inhibitor

The investigational drug product NKTR-102 for Injection is formulated as a sterile lyophilized powder of NKTR-102 in lactate buffer at pH 3.5, intended for dilution with commercially available 5% Dextrose Injection (w/w%; D5W) or 0.9% Sodium Chloride for Injection before IV infusion. The pH of the formulation is in the range of 3.2 to 4.2, and NKTR-102 for Injection storage condition is 2°C - 8°C, with a shelf-life of 48 months.

Both 5% Dextrose Injection and 0.9% Sodium Chloride for Injection will be locally sourced at each clinical study site.

### 6.2 Packaging and Labeling

NKTR-102 (drug substance) is light sensitive. The lyophilized drug product NKTR-102 for Injection will be supplied in 25 mL Type 1 amber colored glass vials packaged in cartons of 10 vials per carton. Each vial contains lyophilized NKTR-102 equivalent to 100 mg of irinotecan.

Each vial and carton will be labeled to comply with local regulations.

### 6.3 Reconstitution and Handling

NKTR-102 for Injection must be reconstituted with D5W or 0.9% Sodium Chloride for Injection to a final concentration range of 0.2 to 1.6 mg/mL. The reconstituted drug may be stored under ambient lighting conditions at room temperature (15 to 30°C) for up to 6 hours prior to start of infusion. Other drugs must not be added to the infusion solution.

NKTR-102 for Injection must be administered as an IV infusion over approximately 90 minutes ( $\pm$  15 minutes). Premedications are not required to be administered prior to the initial infusion in this study, but may be used for an individual subject, as needed. If a subject has reported symptoms (such as nausea and/or vomiting) in the original study, prophylactic use of anti-emetics may be attempted.

The instructions for reconstitution and administration of NKTR-102 for Injection are described in detail in the Pharmacy Binder.

#### **6.4 Treatment Assignment**

This is an open-label trial. There will be no subject randomization or stratification. Subjects will retain the subject identification numbers assigned in the original protocol.

#### **6.5 Dosage and Administration**

Body surface area (BSA) will be determined before the start of each cycle, based on baseline height and most recent weight. Body surface area may be calculated based on institutional guidelines. NKTR-102 will be administered as an IV infusion over 90 minutes ( $\pm$  15 minutes). The recommended dose and schedule of NKTR-102 is 145 mg/m^2 q21d, with BSA capped at 2.4 m^2. Subjects who were previously receiving the 145 mg/m^2 dose will continue to receive this dose in this extension study in a q21d schedule.

Subjects originally enrolled in a clinical study in which a lower-than-recommended dose was administered (e.g., Protocol 12-102-13 in subjects with impaired liver function) or was being administered after a dose reduction will continue to receive that same dose in a q21d schedule in this study. For Protocol 12-102-13 subjects with hepatic dysfunction, as defined in that study, will continue in this extension study (Protocol 11-PIR-09) to receive the originally assigned dose from the 12-102-13 study in a q21d schedule.

Subjects originally enrolled in a clinical study in which a higher-than-recommended dose was being administered (e.g., Protocol 12-102-12 to explore the effects of NKTR-102 on cardiac function) will receive the recommended dose of NKTR-102 of 145 mg/m^2 in a q21d schedule in this extension study (Protocol 11-PIR-09).

Subjects who underwent dose reduction of NKTR-102 due to observed toxicity prior to participation in the Extension study [Protocol 11-PIR-09] will not be re-escalated to the previous dose level upon resolution of the toxicity.

Dose escalation for NKTR-102 is not permitted.

Refer to the Pharmacy Binder for further information.

## 6.6 Duration of Treatment

The estimated study duration is approximately 5 years. The duration of treatment in this study is estimated to be approximately 2 years. Subjects may continue to receive repeated cycles of study drug treatment until progression of disease, unacceptable toxicity, death, withdrawal by subject, Investigator decision, lost to follow-up, or study is terminated by the Sponsor.

## 6.7 Dose Modifications and Delays

All adverse events (AEs) will be assessed according to the NCI-CTCAE version 4.0. In the event of multiple toxicities, dose delays and modifications should occur in accordance with the worst toxicity observed.

Specific dose modifications for NKTR-102 will be made for diarrhea, dehydration, hematological, and other non-hematological toxicities. Dose delays may be permitted between cycles.

Prior to initiation of subsequent NKTR-102 cycles, subjects must meet requirements with respect to hematopoietic function (hemoglobin  $\geq 8.0$  g/dL or 80 g/L; ANC  $\geq 1.5 \times 10^9$ /L; platelets  $\geq 75 \times 10^9$ /L). Diarrhea must be fully resolved to NCI-CTCAE Grade 0 (a return to normal bowel movement habits) for at least 7 days without supportive antidiarrheal measures prior to retreatment. Any treatment-related non-hematologic toxicities must have resolved to baseline or Grade 1.

If the subject fails to meet the criteria for re-treatment, treatment may be delayed, followed by an additional evaluation to determine feasibility of retreatment. Initiation of subsequent doses may be delayed for a maximum of 28 days to allow recovery from any toxicity to permit retreatment. Subjects whose treatment delays are  $\geq 14$  days but  $\leq 28$  days due to a drug-related toxicity must initiate their next treatment cycle with a dose reduction. Subjects who require  $> 28$  days delay due to unresolved toxicity must be withdrawn from treatment, unless, in the Investigator's opinion, continuing in the study is of benefit for the subject. In this case, the continuation of treatment must be discussed with the Medical Monitor and the reason for continuation must be approved and documented.

Subjects from Protocol 12-102-13 with impaired liver function who are entering the extension study will receive the same dose as that received in the 12-102-13 study. Investigators may choose to reduce the dose of NKTR-102 for either drug-related or non-drug related Grade 3 or higher liver dysfunction only after approval from Nektar Medical Monitor.

Supportive care may be implemented in order to treat diarrhea, nausea, vomiting, anorexia, myelosuppression, and/or other AEs. Dose delays may be implemented to permit recovery if a subject is demonstrating clinical benefit, but with repeated Grade 2 toxicities that would otherwise mandate withdrawal.

Dose reductions may also be implemented for subjects who experience recurrent or specific severe toxicities (see [Table 4](#)). NKTR-102 doses for an individual subject may be reduced by 25 mg/m^2 based on conditions listed in [Table 4](#). Subjects should be discontinued from the study treatment if toxicity would indicate more than 2 dose reductions. Dose re-escalation for NKTR-102 is not permitted.

- For subjects entering this study at a starting dose of 145 mg/m^2: dose reductions to 120 mg/m^2, then to 95 mg/m^2 may occur based on conditions listed in [Table 4](#).
- For subjects (i.e., from Protocol 12-102-13) entering this study at a starting dose of 120 mg/m^2: dose reductions to 95 mg/m^2, then to 70 mg/m^2 may occur based on conditions listed in [Table 4](#).
- For subjects (i.e., from Protocol 12-102-13) entering this study at a starting dose of 95 mg/m^2: dose reduction to 70 mg/m^2 may occur based on conditions listed in [Table 4](#).
- For subjects (i.e., from Protocol 12-102-13) entering this study at a starting dose of 50 mg/m^2: dose reduction should be approved by Medical Monitor.
- [Table 4](#) provides instructions regarding dose modification.
- DURING A CYCLE: [Table 4](#)/Column 2 describes the recommended guidelines for management and supportive care during a cycle of therapy.
- INITIATION OF A SUBSEQUENT CYCLE: [Table 4](#)/Column 3 describes the recommended dose modifications for Day 1 in subsequent cycles of therapy. All dose modifications in a new cycle should be based on the worst toxicity observed in the previous cycle and the dose reduction will be relative to the Day 1 dose of the previous cycle.

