#### 2.1.2.5 Study Drug Discontinuation due to Adverse Events and Physician Decision in Phase 3 BEACON (11-PIR-11) Study

A summary of the most common TEAEs leading to study drug discontinuation (> 1 patient in the NKTR-102 treatment arm) is presented in [Table 2](#). There was a higher overall incidence of TEAEs leading to discontinuation in the NKTR-102 treatment arm (11.1%) compared with TPC (6.7%), and there was a higher incidence of diarrhea leading to discontinuation in the NKTR-102 treatment arm (3.1%) compared with the TPC treatment arm (0%). The incidence of neuropathy leading to discontinuation was higher in the TPC treatment arm (2.2%) compared with the NKTR-102 treatment arm (0.2%).

Strict protocol-mandated diarrhea management guidelines were implemented in the BEACON study, including requirements for removal of patients from the study due to diarrhea. Guidelines were created based on the safety experience obtained in the prior phase 2 program where Grade  $\geq 3$  diarrhea occurred at a rate of approximately 20% (see IB for details). Dose reductions were required to prevent the possibility of accumulation of active drug upon repeated dosing; occurrence of Grade  $\geq 2$  diarrhea was controlled by temporary discontinuation of NKTR-102. The BEACON protocol mandated discontinuation after the third occurrence of Grade  $\geq 2$  diarrhea. Because the incidence of Grade  $\geq 3$  diarrhea is less than 10% with the implementation of diarrhea management guidelines, and given that the median time to resolution for all Grades

of diarrhea was 1.5 days, any subsequent studies will not require treatment discontinuation after 3 episodes of Grade  $\geq 2$  diarrhea.

Also of importance, a greater proportion of patients were removed from NKTR-102 (2.8%) for neutropenia compared to TPC (0.2%), despite the lower rate of Grade  $\geq 3$  neutropenia with NKTR-102 (9.6%) compared with that of TPC (30.6%). The median time to onset of Grade  $\geq 3$  neutropenia was 120 days on NKTR-102 compared with 16 days on TPC. The significance of the difference in time to onset is that the clinical decision to discontinue treatment due to neutropenia likely occurs at a much later time point for patients on NKTR-102, when there may be less clinical benefit to continue; this situation is quite different from an appropriate response to the occurrence of early neutropenia (ie, with TPC), where dose delay is more common.

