Febrile Neutropenia Grade 3 or 4 (ANC <1000/mm  with a single temperature of ≥ 38.3°C (101°F) or a sustained temperature of ≥ 38°C (100.4°F) for more than one hour	Treat as appropriate (eg, growth factor support; antibiotics); consider hospital admission. Patients should be hospitalized for IV antibiotic therapy if sepsis is suspected.	Retreatment must be delayed until the toxicity is Grade ≤ 1. 
 
• ↓ 1 dose level after 1st occurrence. Use prophylactic growth factor therapy.
 
• ↓ 1 dose level after 2nd occurrence. Use prophylactic growth factor therapy.
 
 Discontinue NKTR-102 after 3rd occurrence.
Thrombocytopenia		
Grade 1 or 2		Maintain dose level.
Grade 3 (Platelets ≥ 25, <50K)	Consider platelet transfusion if active bleeding. Following platelet transfusion, retreatment must be delayed for 7 days and patient must meet retreatment criteria prior to dosing.	If present on a treatment day, hold therapy until toxicity resolves to platelets ≥ 50K. 
 
• ↓ 1 dose level after 1st occurrence.
 
• ↓ 1 dose level after 2nd occurrence.
 
 Provided that adequate supportive care has been given to the patient, and the investigator believes it is in the best interest of the patient, retreatment may be attempted for a 3rd episode of Grade 3 thrombocytopenia.
Grade 4 (Platelets < 25K)	Consider platelet transfusion if platelets ≤10K or with active bleeding. Following platelet transfusion, retreatment must be delayed for 7 days and patient must meet retreatment criteria prior to dosing.	If present on a treatment day, hold therapy until toxicity resolves to platelets ≥ 50K. 
 
• ↓ 1 dose level after 1st occurrence.
 
• ↓ 1 dose level after 2nd occurrence.
 
 Discontinue NKTR-102 after 3rd occurrence.
Anemia		
Grade 1 or 2		Maintain dose level

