Grade 2		
 
• ↓ 1 dose level after 1st occurrence; use prophylactic anti-diarrheal supportive care
 
• ↓ 1 dose level after ≥ 2nd occurrence; use prophylactic anti-diarrheal supportive care
 
 Provided that adequate supportive care has been given to the patient, retreatment may be attempted for a 3 rd episode of Grade 2 diarrhea (re-instruct the patient on supportive care).

Toxicity NCI CTCAE Grade	During a Cycle	Dose Modifications for Day 1 of New Cycle
Grade 3/4		
 
• ↓ 2 dose levels after 1st occurrence; use prophylactic anti-diarrheal supportive care
 
 Provided that adequate supportive care has been given to the patient, retreatment may be attempted for a 2nd episode of Grade 3 diarrhea (re-instruct the patient on supportive care).
Dehydration		
Grade 1: Increased oral fluids indicated; dry mucous membranes; diminished skin turgor	Consider anti-emetic or anti-diarrheal supportive care	Maintain dose level; consider prophylactic anti-diarrheal or anti-emetic supportive care
Grade 2: IV fluids indicated <24 hours	Use anti-emetic and/or anti-diarrheal supportive care	Maintain dose level or ↓ 1 dose level after 1 st occurrence; use prophylactic anti-emetic or anti-diarrheal supportive care. 
 
• ↓ 1 dose level after ≥ 2nd occurrence; use prophylactic anti-emetic or anti-diarrheal supportive care.
 
 Provided that adequate supportive care has been given to the patient, retreatment may be attempted for a 3 rd episode of Grade 2 dehydration (re-instruct the patient on supportive care).
Grade 3: IV fluids or hospitalization Indicated; Grade 4: Life-threatening consequences; urgent intervention indicated	Use anti-emetics, anti-diarrheal supportive care, and/or IV fluids as appropriate. Consider hospital admission.	Treatment must be delayed until the toxicity recovered to baseline or Grade < 1. 
 
• ↓ 2 dose levels after 1st occurrence; use prophylactic anti-emetic or anti-diarrheal supportive care.
 
 Provided that adequate supportive care has been given to the patient, retreatment may be attempted for a 2 nd episode of Grade 3 dehydration (re-instruct the patient on supportive care). NKTR-102 must be discontinued for a 2 nd episode of Grade 4 dehydration.

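### Table 4's repeated reductions for Grade 2 diarrhea leave its third-episode retreatment with no valid dose under section 6.7, and Protocol 12-102-13 entrants at 95 mg/m² have no listed dose for a two-level cut

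*Protocol*

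**What the plan says.** **The limit.** Protocol section 6.7 sets one dose level at 25 mg/m² and states: "Subjects should be discontinued from the study treatment if toxicity would indicate more than 2 dose reductions". Each reduction starts from the dose last given: "the dose reduction will be relative to the Day 1 dose of the previous cycle". Section 6.7 lists the reduced doses by entry dose: 120 then 95 for entry at 145; 95 then 70 for entry at 120; 70 only for entry at 95. Reductions from 50 need Medical Monitor approval. The bullets for 120, 95 and 50 name Protocol 12-102-13 subjects.

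**The diarrhea row.** For Grade 2, Table 4 goes down one level after the first occurrence, and the next bullet reads "1 dose level after ≥ 2" (that is, the second occurrence or any later one). The cell then permits retreatment for a third "episode of Grade 2 diarrhea (re-instruct the patient on supportive care"). A first Grade 3/4 diarrhea calls for two levels down.

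**Text that bears on the limit.** Section 6.7 allows dose delays "if a subject is demonstrating clinical benefit, but with repeated Grade 2 toxicities that would otherwise mandate withdrawal". It also says that subjects delayed 14 to 28 days for a drug-related toxicity "must initiate their next treatment cycle with a dose reduction". Section 2.1.2.5, explaining the move away from the Phase 3 rule, says "any subsequent studies will not require treatment discontinuation after 3 episodes of Grade" 2 or higher diarrhea.

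**The concern.** The third Grade 2 diarrhea is where the rules meet. Table 4 permits retreatment and, read literally, attaches a further reduction to it. Section 6.7 says that a third reduction means stopping. The stop rule therefore cancels the permission, against the intent in section 2.1.2.5. An investigator who uses the permission cannot tell whether to repeat the current dose or go to an unlisted one.

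The second gap concerns subjects from the impaired-liver-function study who enter at 95 mg/m². Their first severe event can call for a dose that section 6.7 does not list, and the stop rule does not apply.

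The primary objective is continued access, and section 2.1.2.4 calls gastrointestinal toxicity, especially diarrhea, the most common and clinically significant toxicity. What is at stake is the dose a subject receives, and with it the tabulated discontinuation reasons (SAP 7.1) and dose reductions (SAP 7.5). The SAP plans no hypothesis test, so no inference is affected.

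**Working it through.** **Inputs.** Step size, dose lists, stop rule and cumulative rule: Protocol 6.7. Reductions per occurrence: Table 4. Assumption: no reduction was used before entry.

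**Formula.** Dose after k levels = entry dose − 25k. The stop rule applies when k > 2.

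**Step 1: reproduce the listed doses.** 145 − 25 = 120 and 120 − 25 = 95. 120 − 25 = 95 and 95 − 25 = 70. 95 − 25 = 70. All match section 6.7.

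**Step 2: Grade 2 diarrhea, read literally.**

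| Entry (mg/m²) | 1st episode | 2nd | 3rd | 3rd dose listed? | Stop rule at 3rd? |
|---|---|---|---|---|---|
| 145 | 120 | 95 | 70 | No | Yes (k = 3) |
| 120 | 95 | 70 | 45 | No | Yes (k = 3) |

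The third-episode dose would be 70/145 = 48.3% or 45/120 = 37.5% of the entry dose.

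**Step 3: compare the other rows.** Six other rows allow third-episode retreatment: Grade 2 neutropenia, Grade 3 neutropenia, and Grade 3 thrombocytopenia, anemia, nausea/vomiting/abdominal pain and other drug-related non-hematologic toxicity. The thrombocytopenia row, for example, says "retreatment may be attempted for a 3rd episode of Grade 3 thrombocytopenia". All six name reductions for the first and second occurrence only (in some cases conditional), so the third indicates no further reduction and k stays at 2 or below. They do not conflict with section 6.7.

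**Step 4: Grade 2 dehydration.** This row also reduces at every occurrence from the second on, but its first reduction is optional. From 145:
- First reduction not taken: 145, 120, 95 after episodes 1 to 3. k = 2, no conflict.
- First reduction taken: 120, 95, 70. k = 3, same conflict as diarrhea.

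**Step 5: entry at 95 mg/m² (Protocol 12-102-13).** Table 4 calls for two levels down after a first Grade 3/4 diarrhea, a first Grade 3/4 dehydration, a first Grade 4 nausea/vomiting/abdominal pain, or a first Grade 4 other drug-related non-hematologic toxicity. 95 − 50 = 45, which is 45/95 = 47.4% of the entry dose and is not listed. k = 2 is not more than 2, so the stop rule does not apply. Two single-level reductions (70, then 45) reach the same point. From 145 and 120 a two-level cut gives 95 and 70, both listed.

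**Step 6: does the softening text supply a dose?** The delay sentence names no dose and does not waive the limit. A drug-related delay of 14 to 28 days itself requires a reduction, which for a subject already reduced twice leads back to the stop rule. Exclusion criterion 2, which bars subjects with two reductions and a toxicity needing another, shows that the limit is meant.

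**The case against.** The best defence is that the texts can be harmonised. The stop sentence uses *should*, section 6.7 describes the third column of Table 4 as recommended modifications, and the retreatment sentence is a specific permission. Taken with the six parallel rows and section 2.1.2.5, the likely intent is at most two reductions, then optional retreatment at the dose reached. That is probably right. But the diarrhea row does not say it, and the literal wording points to a third reduction and hence to stopping.

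A reader might infer that a site cannot comply with both texts at all. The documents do not support that: retreatment is optional, so a site that stops breaches nothing. The defect is that the permission has no dose attached and is overridden by the limit.

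A reader might also infer that different handling across sites is itself the fault. Table 4 leaves retreatment to the investigator in many rows, and Investigator decision is a listed reason for stopping. Sites may still legitimately differ after the fix; what becomes settled is the dose.

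For 95 mg/m², the single listed step suggests that 70 is the floor. SAP 5.2 also uses 70 as the floor for continuing a lower dose, but it follows an earlier protocol amendment, and the current protocol admits entrants at 50. Even with 70 as the floor, it remains open whether a two-level call means give 70 or stop. Nor does the gap reach everyone at 95: a subject already reduced from 145 to 95 has used both reductions, and a further one falls under the stop rule.

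**Conclusion.** The wording should be corrected. For entry at 145 or 120 mg/m², a third Grade 2 diarrhea indicates a third reduction, to 70 or 45, at which section 6.7 says treatment should stop. This voids the permission in Table 4. Grade 2 dehydration conflicts only if its optional first reduction was taken. For Protocol 12-102-13 subjects entering at 95, a two-level call leaves three readings open: give 70, give 45, or stop.

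The number affected is unknown, because the documents give neither third-episode counts nor the number entering at 95. A reader might take the Phase 3 diarrhea figures in Table 1 as a size: 14.8% + 9.6% = 24.4% had a worst grade of 2 or 3. That is not a rate of third episodes, and it comes from a different population; extension subjects have already received the drug without progression. Nor does anything here invalidate an analysis: SAP 7.1 and 7.5 count what happened, and there is no test. The consequence is limited to individual dosing and those descriptive counts.

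**What to change.** 1. **Grade 2 diarrhea row.** Replace *≥ 2nd* with *2nd*, as in the six other rows, and state that any retreatment after a third episode is at the current dose with no further reduction. Whether to retreat stays with the investigator. If the 14-to-28-day delay rule would require a third reduction, the stop rule applies.
2. **Grade 2 dehydration row.** State that reductions stop at two levels in total and that later retreatment is at the current dose.
3. **Section 6.7.** Keep the stop sentence and add that a two-level drop counts as two reductions.
4. **Section 6.7, Protocol 12-102-13 subjects entering at 95 mg/m².** State that 70 is the lowest dose level, and that when Table 4 calls for a lower dose, treatment stops unless the Medical Monitor approves a dose, in line with the bullet for 50 mg/m² entrants. For these subjects this takes precedence over items 1 and 2.

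The cost is a wording change to two Table 4 cells, one added sentence and one bullet. It needs IRB/IEC approval (Protocol 13.1) across up to 100 sites, but can be bundled with the next amendment. Sample size, data collection and analysis do not change.

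### A third Grade 2 diarrhea episode falls under two incompatible instructions: the two-reduction limit in Protocol Section 6.7 ends treatment, while Table 4 permits retreatment

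*Protocol*

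**What the plan says.** Four places in the protocol bear on the point.

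- **Section 6.7, general limit.** "Subjects should be discontinued from the study treatment if toxicity would indicate more than 2 dose reductions". One step is 25 mg/m²: "doses for an individual subject may be reduced by 25 mg/m 2 based on conditions listed in" Table 4. For a start at 145 mg/m² the section names two lower doses and no third: "dose reductions to 120 mg/m 2 , then to 95 mg/m 2 may occur based on conditions listed in" Table 4. Steps accumulate, because "the dose reduction will be relative to the Day 1 dose of the previous cycle".
- **Table 4, Grade 2 diarrhea and dehydration.** For diarrhea the first instruction is "1 dose level after 1 st occurrence; use prophylactic anti-diarrheal supportive care", and the second is "1 dose level after ≥ 2 nd occurrence; use prophylactic anti-diarrheal supportive care". The row then adds "Provided that adequate supportive care has been given to the patient, retreatment may be attempted for a 3"rd episode of Grade 2 diarrhea. For dehydration the first-occurrence reduction is optional (the dose may be kept or lowered one level). After that the row uses the same "dose level after ≥ 2"nd wording and the same permission to retreat for a third episode.
- **Section 2.1.2.5, background.** The Phase 3 study had to stop treatment after a third Grade 2 or higher diarrhea. The section says that later studies will not carry that requirement.
- **Section 6.7, earlier paragraph.** For subjects with clinical benefit and recurring Grade 2 toxicity of a kind that would otherwise force withdrawal, dose delays are allowed.

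None of these places says which rule takes precedence over the others.

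**The concern.** Two sites could each follow the protocol to the letter and treat the same subject differently. At the third Grade 2 diarrhea, one would stop treatment under the Section 6.7 limit and the other would re-dose under Table 4. The event is not remote: Section 2.1.2.4 names gastrointestinal toxicity, diarrhea above all, as the most common and clinically significant toxicity of the drug, and Section 6.6 expects treatment to last about two years.

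Subject safety comes first. The split would also feed the reasons for discontinuation (SAP 7.1), the counts of dose reductions with reasons and the relative dose intensity (SAP 7.5), and the adverse event summaries by dose level (Protocol 12.2). Part of what those tables show would then be site interpretation rather than tolerability.

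**Working it through.** The check is a count of cumulative reductions by episode, compared with the limit of 2. No sample size, power or error rate is involved.

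**Inputs.** Limit of 2 reductions, 25 mg/m² per level, each step taken from the previous cycle's Day 1 dose (Section 6.7). Levels per occurrence come from Table 4. The subject is assumed to start at 145 mg/m² with no reductions for any other reason.

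**Formula.** Cumulative reductions after episode n = (levels at the 1st) + (n − 1) × 1, because the second-or-later wording takes one level each time. Implied dose = 145 − 25 × cumulative reductions.

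| Grade 2 row | 1st | 2nd | 3rd | 4th |
|---|---|---|---|---|
| Diarrhea | 1 (120) | 2 (95) | **3 (70)** | 4 (45) |
| Dehydration, reduced at 1st | 1 (120) | 2 (95) | **3 (70)** | 4 (45) |
| Dehydration, maintained at 1st | 0 (145) | 1 (120) | 2 (95) | **3 (70)** |

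Entries are cumulative reductions, with the implied dose in mg/m² in brackets. Bold marks the first count above 2.

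- **Diarrhea.** The third episode gives 1 + 1 + 1 = 3 > 2. Section 6.7 discontinues; the Table 4 row permits retreatment. The implied 70 mg/m² is not among the steps listed for a 145 mg/m² start.
- **Dehydration.** The result is the same at the third episode if the first reduction was taken. If the dose was kept, three episodes give 0 + 1 + 1 = 2, which is within the limit; the count passes the limit at the fourth (0 + 1 + 1 + 1 = 3).
- **Comparison rows.** Grade 2 and 3 neutropenia, Grade 3 thrombocytopenia, Grade 3 anemia and Grade 3 nausea/vomiting/abdominal pain list reductions only after the first and second occurrence, without the ≥ sign. They total at most 1 + 1 = 2, so retreatment for a third episode there does not by itself pass the limit.

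**Do the other two places settle it?** Section 2.1.2.5 fits Table 4 and not the limit, because the limit read with the diarrhea row does require stopping at the third episode. The earlier paragraph of Section 6.7 allows delays only and leaves the limit in place. That section also requires a reduction after a drug-related delay of 14 to 28 days, so a delay can itself add to the count.

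**Size.** The share of subjects with three or more Grade 2 episodes is not given. The nearest figure is Protocol Table 2: diarrhea was the reason for stopping in 13 of 425 Phase 3 patients, under a rule that mandated stopping after the third Grade 2 or higher episode. 13 / 425 = 3.1%, and 0.031 × 150 ≈ 4.6, or about 5 subjects at the enrollment ceiling.

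**The case against.** The best answer is that the texts can be harmonized, in one of two ways.

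1. *The limit sits over the table.* Section 6.7 describes the new-cycle column of Table 4 as recommended modifications, retreatment is only permitted, the 145 mg/m² ladder ends after two steps, and exclusion criterion 2 in Section 5.2 uses the same two-reduction threshold. But in the diarrhea row the reductions at the first and second episodes already use up the limit. Under this reading the permission to retreat for a third episode could never apply.
2. *The second-or-later wording means one further reduction in all, with retreatment at an unchanged dose.* That would keep the total at two. It requires reading past the ≥ sign, which the comparison rows do not carry, and nothing in the protocol says that it is meant this way.

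Either reading may be what was intended, and a site could adopt either in good faith. What stands is that neither is written down. The conflict does rest on the literal sense of one symbol, which makes this an inconsistency of wording that can be cured by wording.

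It is also fair to say that the affected tables are descriptive. The listed endpoints are toxicity incidence and duration, and tumor response (Protocol 4.1.1, SAP 4.1). SAP 6.1 plans no hypothesis test, and the tables would still record what was done and why.

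**Conclusion.** The point holds for Grade 2 diarrhea at the third episode. For Grade 2 dehydration it holds at the third episode if the dose was lowered at the first, and otherwise at the fourth. It rests on the literal reading of the second-or-later wording and on a subject with no reductions for other reasons; reductions for other toxicities would bring the limit forward.

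The number affected is unknown. About 5 of up to 150 is an illustration only: not all 13 Phase 3 stops need have followed a third episode, and extension subjects are a selected group with longer exposure.

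Three stronger inferences are not supported:

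- **That dehydration always conflicts at the third episode.** Its first reduction is optional.
- **That every row allowing a third retreatment breaks the limit.** The comparison rows stop at two reductions.
- **That about 22 subjects are affected (0.148 × 150, from the Grade 2 column of Protocol Table 1).** That figure counts anyone whose worst diarrhea was Grade 2, including those with a single episode.

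The consequence is uneven practice on stopping and dose, with some blurring of descriptive summaries. No inferential result is at risk. The correction should be made, because sites following the plan exactly can now diverge on the drug's most common toxicity.

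**What to change.** Reconcile Section 2.1.2.5, both parts of Section 6.7 (the two-reduction limit and the paragraph on repeated Grade 2 toxicity) and the Grade 2 diarrhea and dehydration rows of Table 4. The revised text should state:

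- for each of the two rows, what happens to dose and to treatment at the third and at later episodes;
- whether the second-or-later wording means one further reduction or one at every recurrence;
- whether the Section 6.7 limit overrides Table 4 or the reverse.

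Which rule to adopt is for the clinical team. The cost is a wording change in the protocol or a clarification letter to sites; no change to data collection or to the planned analyses is needed.
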